6.1.1 Non-Hematologic Toxicities of Entinostat

The following rules will be followed for the management of adverse events that are definitely or probably due to entinostat alone. Grades are according to the active version of NCI CTCAE as per section 7.3.

Toxicity	Hold dose	Treatment	Recovery	Dose reduction
Grade ≥ 3	Until recovery to grade 1 or baseline	Symptomatic remedies, start prophylaxis	If recovered by next scheduled dose	Resume at one dose level below the current dose
			If not recovered by next scheduled dose	Skip this dosing; resume at one dose level below the current dose after recovery
Recurrent Grade ≥ 3 despite dose reduction	Until recovery to grade 1 or baseline	Symptomatic remedies, start prophylaxis	If recovered by next scheduled dose	Resume at one dose level below the current dose
			If not recovered by next scheduled dose	Skip this dosing; resume at one dose level below the current dose every other week after recovery
Grade ≤ 2	Until recovery to grade 1 or baseline	Symptomatic remedies, start prophylaxis	If recovered by next scheduled dose	Resume at the current dose level
			If not recovered by next scheduled dose	Skip this dosing; resume at the current dose after recovery

The dose modification schemas are as follow for both postmenopausal and premenopausal women:

Dose Modification Schema for Postmenopausal Women		
Dose Level	Dose	
	Entinostat (mg)	Anastrozole (mg) daily
-1	3 mg weekly (on day 1, 8, 15, 22, and 29)	1
1	5 mg weekly (on day 1, 8, 15, 22, and 29)	1

or

Dose Modification Schema for Premenopausal Women		
Dose Level	Dose	
	Entinostat (mg)	Tamoxifen (mg) daily
-1	3 mg weekly (on day 1, 8, 15, 22, and 29)	20
1	5 mg weekly (on day 1, 8, 15, 22, and 29)	20

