5.8 Criteria for Removal from Study

Patients will be removed from study when any of the criteria listed below applies. The reason for study removal and the date the patient was removed must be documented in the case report form.

- Evidence of rapid disease progression during treatment at the discretion of the treating investigator.
- Non-compliance with the study protocol; including, but not limited to not attending the majority of scheduled visits. The Protocol Chair will determine when non-compliance should lead to removal from study.

Note: The patients will still be included in the overall evaluation of response (intent-to-treat analysis).

- Unacceptable major toxicity or the dosing delay and/or delay in the surgery ≥ 2 weeks.

Note: The patients will still be included in the overall evaluation of response (intent-to-treat analysis).

- Intercurrent illness or condition that would, in the judgment of the treating investigator, affect assessment of clinical status to a significant degree or require discontinuation of study treatment.
- At subject's own request.

Note: The reason for discontinuation from the study must be documented. The patients will be included in the overall evaluation of response (intent-to-treat analysis) if any protocol therapy was administered prior to withdrawal.

- Study is closed for any reason (e.g. new information shows that the patient's welfare would be at risk if she continued study treatment).
- Subject withdraws consent for follow-up.
- Subject is lost to follow-up.
- Study is terminated for any reason.

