6.1.2 Hematologic Toxicities of Entinostat

Myelosuppression is a common side effect of higher doses of entinostat. The guidelines in the table below will be followed for hematologic toxicities.

ANC at planned dose	PLT at planned dose	Cycle Delivery
≥ 1.0 x 10 ⁹ /L	and ≥ 80 x 10 ⁹ /L	Resume at the current dose level
< 1.0 x 10 ⁹ /L	or < 80 x 10 ⁹ /L	Delay until recovery to grade 1 or

baseline

If the treatment is delayed for more than 2 weeks, the patient will be discontinued from treatment and followed until event resolution, and treated off-protocol at the investigator's discretion.

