6.1.3 Toxicities likely from both drugs (diarrhea, anorexia, fatigue, and nausea)

In the event that one of the above toxicities occurs, patients should be treated symptomatically and prophylactic treatment should be considered for subsequent administration of entinostat. In case grade 3 or 4 toxicity is observed both drugs should be held until recovery to grade 1 or baseline.

If dosing is to be delayed by more than 2 weeks the patient will go off study.

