6.2.2 Diarrhea

Diarrhea should be treated promptly with appropriate supportive care, including loperamide. Instruct patients to begin taking loperamide at the first signs of: 1) poorly formed or loose stool; 2) occurrence of more bowel movements than usual in one day; or, 3) unusually high volume of stool. Loperamide should be taken in the following manner: 4 mg at first onset of diarrhea, then 2 mg after each unformed stool. Daily dose should not exceed 16 mg/day. Advise patients to drink plenty of clear fluids to help prevent dehydration caused by diarrhea. Avoid loperamide if there is the presence of blood or mucus in the stool or if diarrhea is accompanied by fever. If grade 3 or 4 diarrhea recurs despite treatment, discontinue further treatment with entinostat.

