12.2 Sample Size/Accrual Rate

For the pilot phase, the study will require 12-24 patients to complete, allowing for 3-6 patients per dose level and 2 predefined dose levels for 2 combination treatments (entinostat and anastrozole as well as entinostat and tamoxifen). In the phase II period, the study will require 12-35 patients to complete. However, we will include the 12 patients in the pilot phase that are treated with the recommended dose level of each combination for phase II in the primary endpoint analysis. Therefore, the total sample size for this study is 12-41 patients. At an anticipated accrual rate of 15-20 patients/year, we anticipate that the phase II part will need to accrue patients for anywhere from 7 to 33 months.

NOTE: The maximum total sample size will most likely remain 41 patients. The only situation that this trial will require additional 6 patients is that there are ≥ 2 patients in the first cohort of 6 patients suffer DLT in dose level 1 in both combination treatments. As of November 2011, there were 3 patients enrolled in the pilot phase of this study. There is no DLT observed in this first 3 patients treated with entinostat and anastrozole. Furthermore, a phase II study of

entinostat and AIs including anastrozole was recently completed which demonstrated that this combination is safe and tolerable with the majority of AEs being only grade 1 or 2⁴⁷. Taken this together, it is highly unlikely that there will be ≥ 2 patients in the first cohort of 6 patients suffer DLT in dose level 1 in entinostat and anastrozole group.

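### The dose-modification and removal rules conflict in three places: no level exists below -1, recurrent diarrhoea has two incompatible instructions, and a delay of exactly two weeks is treated differently across sections.

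*Combined protocol and SAP*

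**What the plan says.** **Dose levels.** The dose tables in the Schema and in sections 5.1, 5.2.1, 6.1.1 and 12.1 all list two entinostat levels: 1 (5 mg weekly) and -1 (3 mg weekly). Section 12.2 counts "2 predefined dose levels for 2 combination treatments".

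**Section 6.1.1.** The table covers non-hematologic events attributed, definitely or probably, to entinostat by itself. After a first event of grade 3 or higher it says "Resume at one dose level below the current dose". The row for events that recur after a reduction carries the same instruction. If the patient has not recovered by the next scheduled dose, that row adds an every-other-week frequency.

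**Diarrhoea.** Section 6.2.2 says: "If grade 3 or 4 diarrhea recurs despite treatment, discontinue further treatment with entinostat". Section 6.1.3, which names diarrhoea among the toxicities likely from both drugs, says: "In case grade 3 or 4 toxicity is observed both drugs should be held until recovery to grade 1 or baseline". It does not address recurrence.

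**Delay.** Section 5.8 lists as a ground for removal "Unacceptable major toxicity or the dosing delay and/or delay in the surgery", with a threshold of two weeks or longer. Section 6.1.2 says: "If the treatment is delayed for more than 2 weeks, the patient will be discontinued from treatment". Section 6.1.3 also acts only beyond two weeks, 6.1.4 permits an interruption of up to 14 days, and 10.3 permits a two-week delay and discontinues only beyond it. For surgery, section 12.3 counts delays longer than two weeks.

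**The concern.** These rules tell a site whether a patient with toxicity restarts, at what dose, and when she comes off. In a multi-center study they have to be executable and to agree with one another. As written, one row of 6.1.1 points to a dose that the protocol never defines, one toxicity has both a stop rule and a resume rule, and one length of delay leads both to removal and to continuation. Two sites that each follow the text faithfully could manage the same patient differently. What is at stake is patient safety and consistent conduct. The second cohort, treated until disease progression, has the longer exposure in which an event could recur.

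**Working it through.** No sample size, power or error rate enters this point, so the check is to trace each rule and set the passages side by side.

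**1. Reduction path under 6.1.1**

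| Level when the event occurs | Event | Instruction | Resulting level |
|---|---|---|---|
| 1 | first grade 3 or higher | one level lower | -1 (defined) |
| -1, after that reduction | recurrence | one level lower | none defined |
| -1, as assigned level | first grade 3 or higher | one level lower | none defined |

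A patient in the recurrence row has by definition already been reduced. With two levels she is at -1 or lower, so both branches of the row point to a level that does not exist. The every-other-week frequency in the not-recovered branch is also absent from every dose table, all of which give weekly dosing.

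The third line of the table is possible because 5.2.1 provides for de-escalation to level -1 and 5.1 leaves the phase II level to be set after the pilot. The path can fit within the first cohort's 29 days: an event after day 1, a reduced dose on day 8, a recurrence before day 15.

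**2. Recurrent grade 3-4 diarrhoea**

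| Section | Applies when | Instruction on recurrence |
|---|---|---|
| 6.1.1 | event attributed to entinostat alone; diarrhoea not excluded | resume one level lower |
| 6.1.3 | toxicity likely from both drugs | none given; hold both drugs at a grade 3 or 4 event |
| 6.2.2 | diarrhoea recurring despite treatment | discontinue entinostat |

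Holding at an event (6.1.3) and discontinuing on recurrence (6.2.2) can be applied one after the other. Resuming (6.1.1) and discontinuing (6.2.2) cannot both be done. The conflict is therefore between 6.1.1 and 6.2.2, for diarrhoea attributed to entinostat alone. Because 6.1.1 already reduces at the first grade 3 or higher event, its instruction here also leads to the missing level in item 1.

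The introduction to 6.1 asks for the most cautious handling when it is unclear which drug caused an event. That concerns causality and settles neither item.

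**3. A delay of exactly two weeks**

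| Section | Delay concerned | At exactly two weeks |
|---|---|---|
| 5.8 | dosing | removed |
| 6.1.2 | dosing | may continue |
| 6.1.3 | dosing | may continue |
| 6.1.4 | dosing | may continue |
| 10.3 | dosing | may continue |
| 5.8 | surgery | removed |
| 12.3 | surgery | not counted towards the de-escalation trigger |

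For dosing, one section stands against four. The boundary can fall on the weekly schedule: a day 8 dose given on day 22 is 22 − 8 = 14 days late. With the ±2-day dosing window in the first-cohort calendar, that dose could be given on days 20 to 24, which is 12 to 16 days late, so exactly 14 days is possible but not fixed.

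**The case against.** The strongest defence is that the affected cases are narrow and that a sensible reader can resolve some of them.

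- **Reach of the missing level.** A reader might infer that every patient starting at level -1, and every patient with a second grade 3 or higher event, is affected. The documents do not support that. A patient at -1 is affected only if a qualifying event occurs. Section 6.1.1 covers only non-hematologic events due to entinostat alone; hematologic, shared and other toxicities follow 6.1.2 to 6.1.4, none of which steps below -1. Section 12.2 reports no dose-limiting toxicity in the first 3 anastrozole patients and regards two or more among that group's first six as highly unlikely. This limits the reach, but the recurrence row still has no defined outcome for a patient it describes.
- **Diarrhoea.** A reader might see a three-way contradiction that includes 6.1.3. That section is silent on recurrence and compatible with 6.2.2. One can also argue that 6.2.2, as the event-specific text, prevails over 6.1.1. That is a reasonable reading, but the protocol states no precedence, and 6.2.2 sits under supportive care rather than dose adjustment.
- **Two-week boundary.** A reader might call this a common case because dosing is weekly. No frequency is given, the dosing window blurs the interval, and 6.1.1 speaks of skipping a dose rather than delaying it, so equating two skipped doses with a 14-day delay is an inference. The mismatch in wording remains.
- **Tissue for the primary endpoint.** A reader might infer that these conflicts decide who provides the post-treatment sample. Section 9.1.1 still seeks tissue from first-cohort patients who stop early and receive other preoperative treatment. Sections 5.1 and 9.1.1 ask for an attempted biopsy in second-cohort patients who stop before day 15. Section 5.8 keeps patients removed for toxicity or delay in the evaluation of response. In the second cohort the biopsy is due by day 29, so later dosing conflicts cannot affect it. An attempt is not a guarantee, but the documents do not support a claimed loss of endpoint data.

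**Conclusion.** The point holds as three specific conflicts in current protocol text.

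1. Section 6.1.1 gives no executable instruction for a recurrent grade 3 or higher event after reduction, or for a first such event in a patient already on level -1.
2. Sections 6.1.1 and 6.2.2 give incompatible instructions for recurrent grade 3-4 diarrhoea attributed to entinostat alone.
3. At a dosing delay of exactly two weeks, 5.8 disagrees with 6.1.2, 6.1.3, 6.1.4 and 10.3. For surgical delay, 5.8 and 12.3 set the boundary differently.

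These are stated rules that cannot be followed or that contradict each other, rather than missing detail. The consequence is inconsistent safety management between sites. The documents give no event rates, so the number of patients affected cannot be estimated. The conclusion assumes that the text means what it literally says where no order of precedence is given.

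**What to change.** Reconcile the passages:

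- Section 6.1.1 should state what applies when no lower dose level exists, and its every-other-week branch should be made consistent with the dose tables.
- Sections 6.1.1, 6.1.3 and 6.2.2 should give one instruction for recurrent grade 3-4 diarrhoea, or state which section prevails.
- Sections 5.8, 6.1.2, 6.1.3, 6.1.4, 10.3 and 12.3 should use one two-week boundary.

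Which clinical rule applies in each case is for the sponsor to decide. The cross-reference in 5.1.1, which points to 6.2 for dose reductions that are set out in 6.1, can be corrected at the same time.

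The cost is a wording amendment to sections 5, 6, 10.3 and 12.3. Sample size and statistical analysis do not change.

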6.1.2 Hematologic Toxicities of Entinostat

Myelosuppression is a common side effect of higher doses of entinostat. The guidelines in the table below will be followed for hematologic toxicities.

ANC at planned dose	PLT at planned dose	Cycle Delivery
≥ 1.0 x 10 ⁹ /L	and ≥ 80 x 10 ⁹ /L	Resume at the current dose level
< 1.0 x 10 ⁹ /L	or < 80 x 10 ⁹ /L	Delay until recovery to grade 1 or

baseline

If the treatment is delayed for more than 2 weeks, the patient will be discontinued from treatment and followed until event resolution, and treated off-protocol at the investigator's discretion.

6.1.3 Toxicities likely from both drugs (diarrhea, anorexia, fatigue, and nausea)

In the event that one of the above toxicities occurs, patients should be treated symptomatically and prophylactic treatment should be considered for subsequent administration of entinostat. In case grade 3 or 4 toxicity is observed both drugs should be held until recovery to grade 1 or baseline.

If dosing is to be delayed by more than 2 weeks the patient will go off study.

6.1.4 Other Adverse Events

For any other NCI-CTCAE Grade 3 or 4 adverse events or any clinically significant, lower-grade adverse event, treatment with entinostat and anastrozole/tamoxifen should be interrupted for a maximum of 14 days until the patient recovers completely or the adverse event reverts to NCI-CTCAE Grade 1 or to baseline grade. If recurrence of adverse event after drug holiday / interruptions is observed a dose reduction to dose level -1 is recommended. Dose reduction should only be implemented when all supportive care measures have been exhausted without an improvement of patient status. In all cases where the subject is withdrawn due to unusual or unusually severe adverse event considered related to entinostat, the investigator must report the withdrawal as an SAE.

6.2 Supportive Care Guidelines

6.2.1 Dehydration/dysgeusia

In other studies, the use of popsicles and Gatorade has been found to be useful by some investigators in maintaining adequate hydration in the setting of dysgeusia.

6.2.2 Diarrhea

Diarrhea should be treated promptly with appropriate supportive care, including loperamide. Instruct patients to begin taking loperamide at the first signs of: 1) poorly formed or loose stool; 2) occurrence of more bowel movements than usual in one day; or, 3) unusually high volume of stool. Loperamide should be taken in the following manner: 4 mg at first onset of diarrhea, then 2 mg after each unformed stool. Daily dose should not exceed 16 mg/day. Advise patients to drink plenty of clear fluids to help prevent dehydration caused by diarrhea. Avoid loperamide if there is the presence of blood or mucus in the stool or if diarrhea is accompanied by fever. If grade 3 or 4 diarrhea recurs despite treatment, discontinue further treatment with entinostat.

6.2.3 Additional Information

When possible, symptoms should be managed symptomatically. In case of toxicity, appropriate medical treatment should be used (including anti-emetics for nausea/vomiting, anti-diarrheals for diarrhea, as above, etc.).

7. **ADVERSE EVENT REPORTING AND DATA SAFETY AND MONITORING PLAN**

7.1 Adverse Events (AEs)

An Adverse Event is any untoward occurrence reflecting a change from baseline state after signing informed consent and up to 30 days from last administration of the study medication. A Serious Adverse Event (SAE) is any AE that is 1) Fatal, 2) Life Threatening, 3) Requires or prolongs hospital stay, 4) Results in a persistent or significant disability or incapacity. 5) Results in a congenital anomaly or birth defect or 6) Is considered by the Investigator as an important medical event.

7.1.1 The descriptions and grading scales found in the revised NCI Common Terminology Criteria for Adverse Events (CTCAE) version 4.0 (Available through <http://ctep.cancer.gov>) will be utilized for AE reporting. AEs of any grade will be documented in the case report form.

7.1.2 AEs can be “Expected” if described in the Informed Consent or “Unexpected”. The attribution of the AE is Definite if the AE is clearly related to study treatment; Probable if it is likely related to the study treatment; Possible if it is equally likely related to study treatment or to some other circumstance, and Unlikely if most probably some other event was responsible for the adverse event, and Unrelated if the Adverse Event is entirely explained by circumstances not caused by the study medication.

7.1.3 Data Safety Monitoring. The UMGCC Data Safety Monitoring / Quality Assurance Committee will review the study. The specific functions of the DSMB /QAC are contained in the UMGCC Clinical Investigators Handbook, available through http://www.umgcc.org/research/clinical_research.htm which is modeled closely after NCI policies and procedures for example, for adverse event reporting. (See <http://www.ctep.nci.nih.gov>.)

7.2 Expedited reporting of severe adverse events

The University of Maryland IRB has specific guidelines for expedited adverse event reporting. These policies can be found in the IRB’s policies and procedures manual which can be accessed using the following URL: <http://www.hrpo.umaryland.edu/default.asp>. The UM policy requires that any harm experienced by a subject or other individual, which in the opinion of the investigator is unexpected and probably related, be expeditiously reported to the IRB within 5 business days.

For those events that require a change to the informed consent, the data entry staff who input these data will notify the appropriate research coordinator and regulatory coordinator of this change.

7.3 Expedited reporting by investigator to Syndax

Serious adverse events (SAE) are defined above. The investigator must inform Syndax in writing using a SAE form or MEDWATCH 3500A form of any SAE within 24 hours of being aware of the event. The date of awareness should be noted on the report. The written report must be completed and supplied to Syndax by facsimile within 24 hours/1 business day at the latest on the following working day. The initial report must be as complete as possible, including details of the current illness and (serious) adverse event, and an assessment of the causal relationship between the event and the investigational product(s). Information not available at the time of the initial report (e.g., an end date for the adverse event or laboratory values received after the report) must be documented on a follow-up report. A final report to document resolution of the SAE is required. If this is a multicenter trial, please participating study sites must report SAEs to Syndax as described and within 24 hours of awareness. Participating sites should also report SAEs to the primary study site.

All SAEs will be reported to Syndax Drug Safety as soon as possible, but no later than fifteen calendar days from first knowledge of the event. A copy will be sent to the FDA (if applicable) by the investigative site:

Syndax Pharmaceuticals, Inc.
Drug Safety/ Regulatory
Attn: [name]
[name]
[name]
[contact]
Main: [contact]
Direct: [contact]

CC: [contact]

8. PHARMACEUTICAL INFORMATION

8.1 Anastrozole

8.1.1 Description

Anastrozole or Arimidex® is a non-steroidal aromatase inhibitor. It is chemically described as 1,3-Benzenediacetonitrile, a, a, a', a'-tetramethyl 5-(1H-1,2,3-triazol-1-ylmethyl) and the molecular formula C₁₇H₁₉N₅, with a molecular weight of 293.4.

8.1.2 Formulation

The tablets are white, biconvex, film-coated containing 1 mg of anastrozole. The tablets are impressed on one side with a logo consisting of a letter "A" (upper case) with an arrowhead attached to the foot of the extended right leg of the "A" and on the reverse with the tablet strength marking "Adx1".

8.1.3 Availability and Storage

The commercial version of anastrozole will be supplied by AstraZeneca Pharmaceuticals.

These tablets are supplied in bottles of 30 tablets of 1 mg anastrozole tablet (NDC 0310-0201-30). Anastrozole should be stored at controlled room temperature, 20-25°C (68-77°F).

Additional information regarding the formulation as well as storage and handling instructions can be found in the approved package insert.

